Protocol Number: Pro00058006

Protocol Title:

Pilot Study of the Endolumik Gastric Calibration Tube for Bariatric Surgery

Sponsoring Company: Endolumik Inc.

Study Site: Duke University

Principal Investigator:

[name] DO FACS FASMBS

Assistant Professor

Duke Center for Metabolic and Weight Loss Surgery

Department of Surgery

Duke University

Durham, NC

Study Site: West Virginia University

Principal Investigator:

[name] MD FACS FASMBS

Associate Professor

WVU Medicine Medical and Surgical Weight-Loss Center

Department of Surgery

West Virginia University

Morgantown, WV

Lay Summary:

Endolumik Inc. has developed a fluorescence-guided calibration device, the Endolumik Gastric Calibration Tube, to improve visualization during bariatric operations. The present pilot study will be a First In Human Investigational Device Exemption (IDE) Clinical Trial to evaluate the Endolumik Gastric Calibration Tube and associated methods in a human clinical cohort of 20-30 bariatric patients at two high-volume bariatric programs. During this clinical study, the single-use, disposable Endolumik Gastric Calibration Tube will be used during twenty sleeve gastrectomy operations and gastric bypass operations. The goal of the present study is to confirm that the Endolumik Gastric Calibration Tube performs similar to predicate devices currently on the market, as well as to get end-user feedback prior to submitting a 510(k) application to the U.S. Food and Drug Administration (FDA).

In this multicenter trial, both study sites are certified as Bariatric Centers of Excellence through the American Society of Metabolic and Bariatric Surgery. The first clinical site is Ruby Memorial Hospital, part of West Virginia University; the second clinical site is Durham Regional Hospital, part of Duke University.

To date, using funding from a West Virginia Clinical & Translational Science Institute Launch Pilot Grant, our team has validated the device and associated methods of

fluorescence-guided sleeve gastrectomy and fluorescence-guided gastric bypass in ex-vivo and in-vivo porcine models, as well as human cadaveric tissue models. Based on FDA criteria, this investigational device meets the definition of a Non-Significant Risk (NSR) device; the risk classification document is included with submission materials.

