The FDA approved predicate device for the Endolumik Gastric Calibration Tube is the VISIGI 3D Sleeve Calibration System With Bulb. Please see attached forms “Predicate Device Information” and “Visigi 3D 510k” for more information.

Device Risk Determination

Based on a careful review of FDA document “Investigational Device Exemptions” 21 CFR 812.3, the relevant guidance documents, and information sheets, it is our determination that the 40F Calibration System does not meet the definition for a Significant Risk (SR) device study [10].

In reviewing the four criteria for a significant risk device, it is determined that:

- The device is NOT intended as an implant
- The device is NOT purported or represented to be for use supporting or sustaining human life
- The device is NOT for a use of substantial importance in preventing impairment of human health
- The device does NOT otherwise present a potential for serious risk to the health, safety, or welfare of a subject

Additionally, the Information Sheet provides in Section X.A several examples of NSR Devices. Among the NSR examples are Conventional Gastroenterology and Urology

Endoscopes and/or Accessories, which are very similar devices to the study device in terms of typical usage and risk.

Given that the device study does not meet the definition of a SR study, it is very similar to example NSR devices, and the proposed use of the device does not introduce significant risk, it is our determination that it is best categorized as a Nonsignificant Risk (NSR) Device Study.

For further information see attached risk determination document.

Relevant Research Team Experience

[name] DO, FACS, FASMBs, principal investigator of the Duke arm of the study, is an Assistant Professor and Bariatric Surgeon at the Duke Center for Metabolic and Weight Loss Surgery. She completed her general surgery residency at SUNY Upstate Medical University in 2014, and a minimally-invasive/bariatric surgery fellowship at Duke University in 2015. She has performed over 1,000 bariatric operations, and helps run the Duke Bariatric Surgery Program, an accredited MBSAQIP Center of Excellence.

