[name], MD, FACS, FASMBs, MBA, principal investigator of the West Virginia University arm of the study, is an Associate Professor and Bariatric Surgeon in the West Virginia University Department of Surgery. He completed his general surgery residency at Loyola University Medical Center in 2012, a postdoctoral research fellowship at Duke University in 2013, and a minimally-invasive/bariatric surgery fellowship at Duke University in 2014. He has performed over 1,000 bariatric operations, and is the Director of the WVU Bariatric Program, an accredited MBSAQIP Center of Excellence.

Subjects:

Details of the population to be included in the study:

- English speaking
- Adult (age 18 to 65)
- Male or female bariatric patients
- Body mass index (BMI) between 35 and 65.99 kg/m²

Inclusion Criteria:

Individuals included in this pilot study are:

- English speaking
- Adults (between age of 18 and 65 years old)
- Have body mass index (BMI) between 35 and 65.99 kg/m²
- Male or female bariatric patients undergoing bariatric surgery at one of the two sites included in the protocol.

Exclusion Criteria are:

Individuals excluded from this study include:

- Nonbariatric patients
- Patients who have conditions that preclude a sleeve gastrectomy or gastric bypass operation
- Patients with esophageal stricture
- Patients with esophageal varices
- Patients with a Zenker's diverticulum
- Patients aged 66 and older
- Patients with a BMI of 66 kg/m² or greater
- Pregnant Women
- Lactating Women
- Other vulnerable patient populations: pregnant and lactating women, prisoners, cognitively impaired and critically ill subjects.

Sample Size:

- The sample size (n) will be 20-30 Bariatric patients.
 - Twenty participants will undergo laparoscopic or robotic sleeve gastrectomy using the Endolumik Gastric Calibration Tube instead of the standard bougie calibration tube.
 - Ten participants will undergo laparoscopic gastric bypass using the Endolumik Gastric Calibration Tube instead of the standard calibration tube.

Sample Size Justification:

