The current pilot protocol is a qualitative, not quantitative, study design, thus no power calculation is indicated. The goal of the present pilot study is to serve as the First In Human IDE trial and confirm that the Endolumik Gastric Calibration Tube performs similar to predicate devices currently on the market, as well as to get end-user feedback prior to 510(k) application to the FDA. The sample size was chosen because 20 to 30 uses will allow the development team to appropriately evaluate device performance.

Study Design and Procedures

1. The study type is prospective and non-randomized.
2. The sample size will be 20-30 Bariatric patients (total between both testing sites) who meet the inclusion criteria listed above.
 - a. Twenty participants meeting inclusion criteria will undergo laparoscopic or robotic sleeve gastrectomy using the Endolumik Gastric Calibration Tube instead of the standard bougie calibration tube. This bariatric operation will take approximately 60 minutes. The amount of time the Endolumik Gastric Calibration Tube will be inside the patient is approximately 20 minutes. The device is removed prior to the conclusion of the operation, while the patient is under anesthesia.

The portions of the sleeve gastrectomy operation where the Endolumik Gastric Calibration Tube will be used include:

- ***To evacuate gastric contents***
- ***During construction of the gastric sleeve***
- ***To perform the leak test of the gastric sleeve***

b. Ten participants meeting inclusion criteria will undergo laparoscopic gastric bypass using the Endolumik Gastric Calibration Tube instead of the standard calibration tube. This bariatric operation will take approximately 120 minutes. The amount of time the Endolumik Gastric Calibration Tube will be inside the patient is approximately 20 minutes. The device is removed prior to the conclusion of the operation, while the patient is under anesthesia.

The portions of the gastric bypass operation where the Endolumik Gastric Calibration Tube will be used include:

- ***To evacuate gastric contents***
- ***During construction of the gastric pouch***
- ***To calibrate closure of the gastrojejunal anastomosis***
- ***To perform a leak test of the gastrojejunal anastomosis***

3. Eligible participants will undergo informed consent.

4. The operative steps for use of the Endolumik Gastric Calibration Tube during the sleeve gastrectomy operation are as follows:

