- m. The Endolumik Gastric Calibration Tube will remain positioned in the stomach during gastric sleeve construction. During sleeve construction, the laparoscopic camera will be changed from white-light mode to NIR mode.

- n. The stomach is divided with a laparoscopic stapler using minimally-invasive staple loads, starting 6cm from the pylorus, taking care not to narrow the stomach at the incisura or the angle of His.
- o. Once the sleeve gastrectomy is completed the the Endolumik Gastric Calibration Tube will be used to perform a leak test. The accessory bulb will be connected to the the Endolumik Gastric Calibration Tube and inflated to the pressure of approximately 35mm Hg. The gastric sleeve will be submerged in saline and evaluate for any leak
- p. The Endolumik Gastric Calibration Tube will be removed under direct visualization.
- q. The surgeon will perform an intraoperative upper endoscopy to examine the gastric sleeve mucosa.
- r. The gastric sleeve operation will be completed in standard fashion.
- s. After completion of the operation the surgeon, surgical assistant, anesthesia providers, and OR nurse will complete a web-based Device Evaluation Form which asks each provider relevant questions regarding their experience with this novel device. (See attached Device Evaluation Form for Gastric Sleeve)

5. The operative steps for use of the Endolumik Gastric Calibration Tube during the gastric bypass operation are as follows:

- a. Informed consent will be obtained at the preoperative clinic appointment. All patient questions will be answered.
- b. Participant will undergo general endotracheal anesthesia in standard fashion.
- c. Once under anesthesia, jelly lubrication will be applied to the Endolumik Gastric Calibration Tube, and it will be gently introduced by the head of be provider through the patient's mouth and oral pharynx and into the esophagus to a distance of 40cm or once gastric content/fluid is visible within tube
- d. A Verress insufflation needle will be inserted into the peritoneum the left upper quadrant abdominal region, confirmation of location will be achieve using a water drop test, (instilling 3ml of water into the needle and confirming a positive meniscus test).
- e. Carbon dioxide insufflation will be connected to the Verress needle and pneumoperitoneum (laparoscopic working space) will be created.

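### The stated goal is to confirm similarity to predicate devices, but the protocol sets out no comparator, reference value or criterion, and only a descriptive analysis

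*Combined protocol and SAP*

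**What the plan says.** The goal is worded the same way in the Lay Summary and the Sample Size Justification: to "confirm that the Endolumik Gastric Calibration Tube performs similar to predicate devices currently on the market". Both places add end-user feedback ahead of a 510(k) application. The Sample Size Justification also calls the study qualitative and says that no power calculation is needed.

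Under Sample Size, "The sample size (n) will be 20-30 Bariatric patients". Sleeve patients are operated on "using the Endolumik Gastric Calibration Tube instead of the standard bougie calibration tube". For bypass, "Ten participants will undergo laparoscopic gastric bypass using the Endolumik Gastric Calibration Tube instead of the standard calibration tube". Study Design and Procedures describes a prospective, non-randomized study and lists three uses of the tube in sleeve cases and four in bypass cases; one of the bypass uses is "To calibrate closure of the gastrojejunal anastomosis".

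The Predicate Device section names one product: "The FDA approved predicate device for the Endolumik Gastric Calibration Tube is the VISIGI 3D Sleeve Calibration System With Bulb". It refers to two attached forms for further information and gives no performance figure.

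Performance is captured by provider survey. For sleeve cases, "After completion of the operation the surgeon, surgical assistant, anesthesia providers, and OR nurse will complete a web-based Device Evaluation Form", and the bypass steps contain a matching item. Data Collection links each form to the patient through the Participant ID. The section on how results will be analyzed is one sentence, promising descriptive statistics for the cohort.

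**The concern.** Confirming that one device performs like another is a comparative conclusion. It needs something to compare with (a control series or a reference value) and a rule, fixed beforehand, for how close is close enough. The protocol text supplies neither. With no rule, nearly any series without a mishap can afterwards be called similar, and the protocol's own wording would support that label in a regulatory submission. The trial's ability to describe how the tube behaves in its first human uses is not in question. What is at stake is the conclusion that may legitimately be drawn from it.

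**Working it through.** **The plan's own figure.** There is no alpha, power, margin or event rate from which to reproduce 20 to 30. The only arithmetic available is 20 sleeve + 10 bypass = 30, which matches the upper end of the range.

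**What a confirmation of similarity would need, set against the text.**

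- *Comparator data.* All sleeve and bypass cases in Sample Size and in Study Design and Procedures use the study tube. No concurrent, historical or matched series is described.
- *Reference value.* None is given for the predicate. The background section quotes a bougie-injury incidence of 0.1-1.2%, but for bougies in general and not as a benchmark. The operation times of about 60 and 120 minutes are planning figures.
- *Criterion.* None. The two events that end the study, under Collection, Assessment and Reporting of Adverse Events, form a safety rule and do not define similarity.
- *Attachments.* The predicate forms and the Device Evaluation Forms are not shown. The text does not say that any of them holds a threshold.
- *Analysis.* Descriptive statistics only.

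**What the planned numbers can describe.** Exact (Clopper-Pearson) two-sided 95% limits, one result per operation, operations treated as independent:

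- All n successful: lower limit = 0.025^(1/n).
- No events in n: upper limit = 1 − 0.025^(1/n).

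| n operations | Lower limit, all successful | Upper limit, no injuries |
|---|---|---|
| 10 | 69.2% | 30.8% |
| 20 | 83.2% | 16.8% |
| 30 | 88.4% | 11.6% |

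**How much an injury-free series shows.** P(no injuries) = (1 − p)^n. Take p = 1.2%, the top of the background range, and p = 5%, an assumed rate about four times higher (5/1.2 = 4.2):

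- n = 20: 0.988^20 = 78.6%; 0.95^20 = 35.8%; ratio 2.2.
- n = 30: 0.988^30 = 69.6%; 0.95^30 = 21.5%; ratio 3.2.

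An injury-free series is therefore only two to three times as likely at the lower rate as at the higher one. Using these rates is an assumption, since the protocol designates neither as a benchmark.

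**The case against.** The strongest reply is that this is a declared qualitative, first-in-human pilot, that the goal is paired with user feedback, and that *similar* means only that the tube does the jobs listed for it. The section on scientific and medical knowledge already speaks of feasibility. Much of this stands: no power calculation is called for, and the functional reading is natural. But the text does not state that reading or say when a job counts as done, and *confirm* still promises more than description.

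A second reply is that the attachments may hold a benchmark. That is possible, and the point is limited accordingly: the protocol does not direct the reader to one.

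Three stronger readings are tempting and are not supported.

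- A reader might infer that no information on the predicate is gathered at all. The Device Evaluation Forms are not shown and may ask providers to rate the tube against their usual device.
- A reader might infer that the named predicate, a sleeve system, does not cover the bypass uses. The attached predicate documents may settle that.
- A reader might infer that several forms per operation will be pooled as independent results. Data Collection ties each form to a participant, and no interval is planned. Nor is the number of forms fixed: the operative steps list four provider roles, while the device-performance item and the handling plan allow fewer.

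**Conclusion.** The point holds as a mismatch between the stated goal and the described design, and it should be fixed before the first case. The missing comparator and criterion decide it; the intervals show only scale. Even a flawless series leaves a function's completion rate compatible with values down to 83.2% in 20 sleeve cases and 69.2% in 10 bypass cases, and an injury rate compatible with values up to 16.8% and 30.8%. Those results are useful as description but do not establish similarity to another device.

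The conclusion rests on the protocol text as published. If an attachment does hold a predicate value and an acceptance threshold, the defect shrinks to a missing citation. It would be too strong to conclude that the study is undersized or not worth running: the documents ask for a descriptive pilot, and the design can deliver one.

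**What to change.** 1. In the Lay Summary and the Sample Size Justification, replace the goal of confirming similarity with one of describing the feasibility, device performance and end-user experience of the tube. This agrees with the feasibility aim stated under scientific and medical knowledge.

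2. In the section on benefits to participants, the protocol asserts outright that the tube is more visible than the standard device. Reword this as an expectation that the study does not test; otherwise a comparative claim remains after the goal is corrected.

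3. As an alternative to item 1, if an attachment already holds a predicate value and acceptance threshold, cite it in the Sample Size Justification and the analysis section before the first case, and name the comparator for sleeve and for bypass.

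4. In the analysis section, state that completion of each device function listed in Study Design and Procedures, and device-related injuries, will be reported by procedure as x/n with exact 95% intervals, where n is the number of operations actually treated. Count each operation once, using the existing Participant ID link, with a stated rule for forms that disagree. Summarize opinion items by provider role.

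The cost is a few sentences, a little analysis work and a more modest stated claim. No patients or procedures are added.

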- p. After completion of the operation the surgeon, surgical assistant, anesthesia providers, and OR nurse will complete a web-based Device Evaluation Form which asks each provider relevant questions regarding their experience with this novel device and monitors for any adverse events. (See attached “Device Evaluation Form for Gastric Bypass”)
- 6. The follow-up period for the study will be 30 days from the date of the bariatric operation.
 - a. Within the postoperative period the patient will follow the standard of care post surgical protocol of each respective site’s bariatric program.
- 7. The following participant outcomes will be recorded:
 - A. Operative time
 - B. Intraoperative adverse events
 - C. 30-day morbidity, specifically any 30-day Metabolic and Bariatric Surgery Accreditation and Quality Improvement Program (MBSAQIP) Occurrences (See attached document “MBSAQIP Occurrences”)
 - D. Video recording of the operation.
 - a. Video storage will be via one of the following: an encrypted harddrive or Epiqar, a HIPAA-compliant system with instant cloud-based surgical video archiving and web-based video conferencing. The Epiqar system interfaces with existing camera equipment in the operating room[11].

8. The following device performance will be gathered:

- A. Device performance data will be collected using de-identified, web based surveys given to surgical team members, anesthesia provider(s), and the operating room team member who unpackages the device.
 - a. The following surveys are included in supplementary materials:
 - i. Device Evaluation Form for Sleeve Gastrectomy
 - ii. Device Evaluation Form for Gastric Bypass

Storage, Handling and Accountability for Investigational Device

The storage plan for the investigational device is as follows: the devices used in the current protocol will be stored in locked, temperature controlled rooms at each study site. At the West Virginia University protocol site this will be the locked, temperature controlled office of the Principal Investigator (PI). At the Duke University protocol site this will be the locked, temperature controlled office of Principal Investigator (PI) [name], DO.

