The handling plan for the investigational device is as follows: the device will be transported to the operating room on the day of the planned bariatric operation by the PI. Once the device is in the operation room, it will be handled and unwrapped by the operating room circulating nurse or the anesthesia provider. Once the bariatric operation is complete, the device will be disposed of in the operating room trash.

In order to ensure accountability of device use, the device will be labeled as investigational use only. Specifically, the device will be labeled in accordance with the labeling provisions of the FDA IDE regulations ([§812.5](#)) and will bear the statement "CAUTION - Investigational Device. Limited by Federal (or United States) law to investigational use."

Scientific / medical knowledge:

This study will demonstrate the feasibility of using a fluorescence-guided calibration device to improve visualization during minimally-invasive bariatric operations and further knowledge regarding the use of fluorescence-guided surgery to improve patient outcomes.

Data Collection

1. Participant data will be collected and stored in a HIPPA Compliant REDCap Database at West Virginia University that will be maintained by the Principle Investigator. (See attached REDCap Form "Pilot Study of Endolumik Device: Participant Registry")
 - o Each consented participant will be assigned a participant ID that will serve as their unique identifier for the duration of the study. The participant ID will be a number from 1 to 30, and will be assigned in chronological order based on the order which subjects are consented for the study (i.e. the first participant enrolled will be assigned Participant ID 1, the final participant enrolled will be assigned Participant ID 30).
2. Device performance data will be collected using a de-identified REDCap Survey (See attached device evaluation forms) that will use the Participant ID as the unique identifier to connect device performance with individual participants.
 - o Clinical providers (surgical team, anesthesia team, operating room staff/nurse) will complete a de-identified web-based questionnaire (Device Evaluation Form) after each operation. The device evaluation form asks each provider relevant questions regarding their experience with this novel device. (See attached Device Evaluation Forms)
 - o The Device Evaluation Forms will be stored in the REDCap participant registry for each corresponding Participant ID.

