3. Participant Demographic Data
 - o Participant ID (assigned as described above)
 - o Study Site
 - o Date of Operation
 - o Surgeon

- o Operation Type
- o Patient Name
- o Medical Record Number
- o Age
- o Sex
- o Height
- o Preoperative Weight
- o Preoperative Body Mass Index (BMI)
- o Past Medical History (hypertension, hyperlipidemia, diabetes, asthma, obstructive sleep apnea, emphysema/COPD, gastroesophageal reflux disease, chronic kidney disease, heart disease, liver disease, venous thromboembolism)
- o Past Surgical History

4. Outcome Data

- o Operative time (minutes)
- o Intraoperative adverse events
- o 30-day morbidity/MBSAQIP Occurrences
- o Device Evaluation Form(s)
- o Video file of operation

How will the results be analyzed?

Descriptive statistics will be calculated for the patient cohort.

Data Monitoring Committee & Data Monitoring Plan

The plan for monitoring data to ensure subject safety (e.g. serious adverse event and unanticipated problem reporting) includes the creation of the following: a formal multidisciplinary Data Monitoring Committee (DMC), a schedule for the DMC to meet, as well as a list of device-related complications that will be monitored for during and after each use of the device.

The Data Monitoring Committee will consist of the following four members: [name] MD, [name] MD, and [name] MBA. The multidisciplinary Data Monitoring Committee (DMC) will meet at regular intervals to ensure no serious adverse events or unanticipated problems arise during device testing, specifically the DMC will meet to review intraoperative outcomes after every 5 patients, and immediately after any adverse events.

Data Monitoring Committee Members

1. **[name] MD, MMM, FASA** is an anesthesiologist and the medical director of Perioperative services for WVU Medicine Children's Hospital. She has more than 30 publications, with several funded studies. She was part of WVU Health Sciences Office of Research Integrity and Subject protection- Institutional Review Board from 2014-2021 and has been a part of numerous study approvals and its review including medical devices. She is also an integral part of the

Children's Hospital Research Consortium which will oversee all research and quality projects at WVU Medicine Children's Hospital.

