2. **[name] MD** obtained her medical degree at Indiana University School of Medicine and completed surgical residency at Ascension Providence Hospital / Michigan State University in Southfield, Michigan. She then completed a Minimally Invasive Surgery Fellowship at the University of California San Diego. Her research interests include clinical outcomes and global health.
3. **[name] MBA** is the Chief Executive Officer of Endolumik Inc. She is a mechanical engineer and seasoned medical device executive, with experience launching medical devices for Johnson & Johnson and Philips Healthcare.

Collection, Assessment and Reporting of Adverse Events

The most important goal of our team during this pilot study is to ensure the safety of the device being tested.

The two adverse events which will signal an immediate end to the study are: (i) if the device leads to an intraoperative perforation of the esophagus or stomach or (ii) if the device is stapled across. If these events were to occur, the study would be ended and a root cause analysis would be performed.

The protocol for recording, reporting and remediating adverse events will be as follows: Following each device use, the clinical providers (surgical team, anesthesia team, operating room staff/nurse) will complete a de-identified web-based questionnaire (Device Evaluation Form). Included in this questionnaire is an area to report any adverse event occurrence. Furthermore, if an intraoperative adverse event occurs, the operating surgeon will notify the study PI immediately following the operation; the PI will arrange for a meeting of the Data Monitoring Committee so that the adverse event can be discussed and a remediation plan can be developed.

Risk to participants:

The risks to participants include the risks of elective surgery which are bleeding, infection, damage to surrounding structures, need for further operations, venous thromboembolism, stroke, heart attack, or death. Furthermore, the potential adverse events associated with bariatric surgeries may include leaks, strictures, ischemia, gastroesophageal reflux disease, chronic pain, dysphagia, and excess weight loss.

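### The DMC's scheduled five-patient review covers intraoperative outcomes only, and the written reporting step that leads to a DMC meeting is triggered only by an intraoperative event, although 30-day occurrences are collected

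*Combined protocol and SAP*

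**What the plan says.** Under Data Monitoring Committee & Data Monitoring Plan, the committee has two kinds of meeting: "specifically the DMC will meet to review intraoperative outcomes after every 5 patients, and immediately after any adverse events". The same section says that the plan includes "a list of device-related complications that will be monitored for during and after each use of the device".

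Under Collection, Assessment and Reporting of Adverse Events, the procedure has two steps. First, the operating room team completes a Device Evaluation Form after each device use: "Included in this questionnaire is an area to report any adverse event occurrence". Second, "if an intraoperative adverse event occurs, the operating surgeon will notify the study PI immediately following the operation". The PI then arranges a committee meeting.

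Study Design and Procedures, item 6, sets the observation window: "The follow-up period for the study will be 30 days from the date of the bariatric operation". During that window patients follow their own site's standard postoperative care. Item 7 lists among the recorded outcomes "30-day morbidity, specifically any 30-day Metabolic and Bariatric Surgery Accreditation and Quality Improvement Program (MBSAQIP) Occurrences". The list under Data Collection, item 4, repeats this as "30-day morbidity/MBSAQIP Occurrences". Participant data go into a "REDCap Database at West Virginia University that will be maintained by the Principle Investigator".

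**The concern.** The study collects one postoperative safety outcome, the 30-day occurrences. That outcome is on no scheduled committee agenda and in no written reporting step. The monitoring plan promises surveillance after device use as well as during it, but the procedure that follows is written for the operating room.

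This matters because the protocol's own background says that tube injuries can cause grave harm, including death, when they are missed during the operation. The Risk to participants section lists perforation, bleeding, fistula and infection among the known tube complications, and nothing confines their recognition to the day of surgery. The device is being used in patients for the first time, and the protocol calls device safety its most important goal.

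The gap also touches a stopping rule. Device-related intraoperative perforation ends the study. If such a perforation is recognised days later, the written notification, timed to the end of the operation, has already passed.

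**Working it through.** The plan has no power, alpha or monitoring boundary that bears on this point, so there is no figure to reproduce. The check is a comparison of the text, a count, and one calculation for context.

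**1. Each monitoring component against a postoperative event**

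| Component | Section | Reaches an event first seen after the operation? |
|---|---|---|
| Scheduled review every 5 patients | Data Monitoring Plan | Not as worded: intraoperative outcomes only |
| Committee meeting after any adverse event | Data Monitoring Plan | Yes, and the meeting is to be immediate |
| Device Evaluation Form | Adverse Events | Open to any adverse event, but completed after device use, with no later update stated |
| Surgeon to PI to committee | Adverse Events | No: the trigger is intraoperative and the timing is the end of the operation |
| 30-day occurrences | Study Design, item 7; Data Collection, item 4 | Recorded, but not linked to the committee |
| Database maintained by the PI | Data Collection, item 1 | Data within reach, but no duty or deadline to review them |

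One component does cover late events, namely the meeting rule. No written step feeds it with a postoperative report.

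**2. Extent**

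- Scheduled reviews: 20 / 5 = 4, or 30 / 5 = 6.
- Outcome items under Data Collection, item 4: 5 (operative time, intraoperative adverse events, 30-day morbidity, evaluation forms, video).
- Postoperative items: 1 of 5. Postoperative items named in the scheduled review: 0 of 1.

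Event-triggered meetings come on top and are not counted.

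**3. Context: how likely is a relevant event at all?**

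The chance of at least one event in n patients is 1 − (1 − p)^n. The rates are those in the protocol's background. The calculation assumes that they apply to this device and, for n = 30, that sleeve leak rates hold for bypass patients too.

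| Event | p | n = 20 | n = 30 |
|---|---|---|---|
| Tube-related injury | 0.1% | 1 − 0.999^20 = 2.0% | 1 − 0.999^30 = 3.0% |
| Tube-related injury | 1.2% | 1 − 0.988^20 = 21.5% | 1 − 0.988^30 = 30.4% |
| Leak | 1% | 1 − 0.99^20 = 18.2% | 1 − 0.99^30 = 26.0% |
| Leak | 2% | 1 − 0.98^20 = 33.2% | 1 − 0.98^30 = 45.5% |

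These are chances of any such event, whenever it is recognised. At the assumed rates they are upper limits for a late-recognised one. The documents do not give the share recognised late, so the chance that an event fails to reach the committee cannot be derived.

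**The case against.** The strongest reply is that the meeting rule already does the work. It requires a meeting immediately after any adverse event, with no restriction to the operating room, and that meeting would usually come before the next five-patient review. The stated purpose of the regular meetings, guarding against serious or unanticipated problems, is also wider than intraoperative outcomes, and nothing forbids the committee from looking at 30-day data. This largely stands. It is why the point is not a serious one. It does not answer who sets the rule in motion for a postoperative event, and a review limited to intraoperative outcomes gives no backstop if the trigger is missed.

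Second, an intraoperative focus is defensible. The tube is in place for about 20 minutes, both stopping events arise in the operation, and every case has a leak test and an endoscopy. At each review the latest patients may still be short of day 30. These facts lower the chance of late recognition but do not remove it. Reviewing what has accrued to date avoids waiting for complete follow-up.

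Third, the attached evaluation forms, the registry form and the list of MBSAQIP occurrences were not available and may name a reporter or deadline. That cannot be excluded.

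A reader might go further and infer that postoperative events are not collected, lie outside the committee's remit, or have no timeline at all. The documents support none of these. Thirty-day occurrences are recorded, the meeting rule includes them, and the time of the meeting is stated. What is missing is the report that should prompt that meeting.

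**Conclusion.** The concern holds in a limited form. The scheduled review is narrower than the safety data the study collects, and the written reporting procedure is narrower than the meeting rule it should serve. A late-recognised tube injury is within the committee's remit but depends on someone reporting it outside the written steps.

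Severity is minor to moderate. The counts (all 4 or all 6 scheduled reviews, 1 postoperative item of 5) measure wording, not risk. The background probabilities should not be read as the chance of a missed event. The conclusion assumes that the scheduled review is read as worded and that no attachment supplies the missing step.

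**What to change.** 1. In the Data Monitoring Plan, add *and all 30-day occurrences accrued to date* to the content of each five-patient review, and add a final review once the last patient completes day 30. The final review is needed because follow-up on the last patients may be incomplete at the last scheduled meeting.
2. In the adverse event section, remove the restriction to intraoperative events, so that the same surgeon-to-PI-to-committee step applies to any adverse event recognised up to day 30. This brings the procedure into line with the existing meeting rule.

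Both are wording changes. The data are already collected and the five-patient meetings already planned. The cost is slightly longer committee packets, one further review (4 + 1 = 5 scheduled reviews with 20 patients, 6 + 1 = 7 with 30), and some meetings about occurrences unrelated to the device. Enrolment need not pause for 30-day data.
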